3.2 Study population and sample size

The study population includes subjects who require locking and flushing the end of catheter line at the intervals of different drug treatment. Specific inclusion and exclusion criteria are described in the 5.2 Selection of subjects of Protocol.

A total of 378 subjects are proposed to be enrolled in this clinical trial. The study is a parallel-controlled, noninferiority design in which the control device is the BD Pre-filled Flush Syringes, a kind of prevalent product already on the market. The study intends to investigate the overall performance of the test device for flushing and/or locking the catheter that shall be non-inferior to that of the control device. Based on previous clinical experience, the overall performance pass rate of control device for flushing and/or locking the catheter is about 98%, and the study assumes the same treatment completion rate for the test device and control device. This study adopts a non-inferiority design, with α =0.025 (one-sided), β =0.1 (power of 90%), and the non-inferiority margin is 5%. The test group and the control group are allocated 1:1 in equal proportions. The sample size shall be calculated by using the PASS software and 165 subjects shall be enrolled into each of the test group and the control group. However, 368 subjects shall be included in this clinical study considering factors such as dropouts (drop-out rate of 10%) during the trial and other factors.

This study will be performed by 63 authorized nurses who participate in using the investigational device, each nurse will randomly use 3 test devices and 3 control devices, so a total of 378 subjects are proposed to be enrolled in this clinical trial.

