6.3 Effectiveness evaluation

6.3.1 Primary effectiveness evaluation

(1) Evaluation Indicators

Overall performance of catheter locking and/or flushing is considered "**pass**" only if: Questions 1 to 4 are answered "Yes" and question 5 is answered "No".

Subjects who do not answer any of questions 1-5 or who answer "not applicable (NA)" will not be entered into the per protocol set; they will be treated in accordance with Table 6.1 when entering the full analysis set.

Table 6.1 Definition of "pass" for different scenarios of primary effectiveness indicators

Questions related to the primary effectiveness indicators	Scenario 1	Scenario 2	Scenario 3	Scenario 4
Whether the effectiveness evaluation is performed?	No	Yes	Yes	Yes
 Whether the air in the pre-filled flush syringe can be removed successfully? Whether the pre-filled flush syringe can be connected to the catheter smoothly? Whether the pre-filled flush syringe can flush and/or lock the catheter successfully? Whether the pre-filled flush syringe can be disconnected from the catheter smoothly? 	NA	Yes	At least one of the answers is "No" for questions 1-4, or "Yes" for question 5	At least one of the answers in Scenario 2 is "NA" or not selected
5. Whether any sites of the flush syringe leak at any time during use?		No		
Primary effectiveness determination (pass/fail)	Missing	Pass	Fail	Missing
Whether to be included in FAS	Yes	Yes	Yes	Yes
Whether to be included in PPS	No	Yes	Yes	No

(2) Evaluation method

The study hypotheses for the primary evaluation indicators are:

Null hypothesis H₀: The overall performance pass rate p_1 in the test device group is inferior to p_2 in the control device group ($p1 \le p2-\delta$);

Alternative hypothesis H₁: The overall performance pass rate p_1 of the test device group is not inferior to p_2 of the control device group $(p_1 > p_2 - \delta)$.

Where $\delta = 5\%$ is the non-inferiority margin, i.e., the range of differences considered not clinically significant.

FAS and PPS are used for evaluation.

Main analysis:

Describe the number and percentage of subjects for whom the two kind of pre-filled flush syringes are used to flush and/or lock the catheter successfully for groups in each study site and all study sites.

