For the primary effectiveness indicator, i.e., overall performance of catheter flushing and/or locking, intergroup comparisons are performed using the Breslow-Day test for parity of effectiveness across sites. The Breslow-Day test is not required if the rate is 100% for both groups in each site, and the effectiveness is considered not statistically different between sites.

A Breslow-Day test with a P > 0.05 means that there is no statistical difference between sites, and the effectiveness data of each site can be combined for analysis. For the difference in the pass rate of the pre-filled flush syringes used to flush and/or lock the catheter in the combined test and control device groups, the 95% confidence interval (CI) for the difference in the pass rate between the two groups is calculated using the Wald method.

A Breslow-Day test with a $P \le 0.05$ indicates a statistical difference between sites, and that the effectiveness data may not be combined for analysis and need to be statistically described separately for each site. Point estimates corrected for site factors are obtained by weighting the difference in the pass rate of the pre-filled flush syringes used to flush and/or lock the catheter by the minimal risk method^[1] for the test device group and the control device group in each site, and the 95% confidence interval (CI) for the difference in the pass rate between the two groups is calculated using the Wald method.

If the pass rate is 100% in both groups, the Newcombe Wilson method ^[2] is used to calculate the 95% confidence interval (CI) for the difference in the pass rate between the two groups.

If the results show that the lower limit of the bilateral 95% confidence interval (CI) for the difference in the pass rate between the test device group and the control device group for pre-filled flush syringes used to flush and/or lock the catheter is greater than -5% (a pre-defined non-inferiority limit), H_0 is rejected and the test device group can be considered non-inferior to the control device group in terms of overall performance pass rate.

The procedure code for calculating confidence interval (CI) about the site-adjusted CMH rate difference is shown below:

/*Variable description: dataset is the input dataset, siteid represents the study site, nurseid represents the nurse, trtp represents the treatment factor, y represents the outcome variable*/

data dataset;

set dataset;

if group="test group" then trt=1;else trt=2;

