  w_diff=beta/s_var_1-(alaph*var_1/(s_var_1+s_advar_1))*(s_betadif/s_var_1);***Calculate the weights
  for rate difference in each site by the minimal risk method;
run;
proc sql undo policy=none;
  create table a riskdiff as
     select *,sum(p1 p2*w diff) as a riskdiff
```

from riskdiff:

```
quit;**Perform weighted estimation of the rate difference between the two groups in each site;
/*****Calculate the confidence interval of rate difference by using Newcombe
                                                                                        and Wald
                               ****
method**
data BinomialCLs1 BinomialCLs2;
  set BinomialCLs;
  if trt=1 then output BinomialCLs1;
  if trt=2 then output BinomialCLs2;
run;
data newcombe0;
merge a riskdiff
BinomialCLs1(keep=siteid LowerCL uppercl
              rename=(LowerCL=LowerCL1 uppercl=uppercl1))
BinomialCLs2(keep=siteid LowerCL uppercl
              rename=(LowerCL=LowerCL2 uppercl=uppercl2));
run;
proc sql undo policy=none;
  create table newcombe as
    select *,sum(LowerCL1*(1-LowerCL1)*w diff**2/sum(n11,n12)) as part1,
          sum(uppercl2*(1-uppercl2)*w_diff**2/sum(n21,n22)) as part2,
          sum(LowerCL2*(1-LowerCL2)*w diff**2/sum(n21,n22)) as part3,
          sum(uppercl1*(1-uppercl1)*w diff**2/sum(n11,n12)) as part4,
          sum(w diff*var) as part
    from newcombe0
quit;* Calculate the prepared parts of the formula by using newcombe and wald methods;
data newcombe wald:
  set newcombe;
  a newcombe l=a riskdiff-probit(1-0.025)*sqrt(part1+part2);
  a newcombe u=a riskdiff+probit(1-0.025)*sqrt(part3+part4):
  a wald l=a riskdiff-probit(1-0.025)*sqrt(part);
  a wald u=a riskdiff+probit(1-0.025)*sqrt(part);
run;*Substitute into the formula;
```

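### The variance printed for the site-weighted branch of the Breslow-Day gate is too large, and the plan names no branch when the test cannot be computed

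*SAP*

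**What the plan says.** The hypotheses in SAP 6.3.1 concern the difference in pass rates, and δ = 5% "is the non-inferiority margin, i.e., the range of differences considered not clinically significant". Before the interval is computed, a Breslow-Day test across the three sites decides how:

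- **P above 0.05.** "A Breslow-Day test with a P > 0.05 means that there is no statistical difference between sites". The sites are pooled and a crude Wald interval is used.
- **P of 0.05 or less.** The text rules out combining the sites, yet goes on to form an overall difference weighted by the minimal risk method, with a Wald interval.
- **Exemption.** "The Breslow-Day test is not required if the rate is 100% for both groups in each site". A Newcombe-Wilson interval is provided only when both groups are at 100%.

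The -5% rule is then applied to whichever interval results. The SAS code printed in the same section obtains the Wald variance of the weighted difference as "sum(w diff*var) as part". Protocol 6.4 has a single confidence interval for the rate difference, with no site test and no branching.

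**The concern.** The test works on odds ratios, while the endpoint and margin are on the rate difference. Near 100% the two scales part: a difference of -2 points is a failure odds ratio of 3.06 at 99% against 97%, but only 1.23 at 90% against 88%. The test also has very few failures to work with, so P above 0.05 says little about agreement between sites.

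The consequences matter more than the choice of test. If the gate opens, the decision rests on an interval whose coded variance is wrong, and a trial with identical results in both arms can miss non-inferiority. If the test has no value, the SAP does not say which interval is primary.

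**Working it through.** **Inputs.** From SAP 3.2: "the overall performance pass rate of control device for flushing and/or locking the catheter is about 98" per cent, with the test device assumed equal; "with α =0.025 (one-sided), β =0.1 (power of 90%), and the non-inferiority margin is 5" per cent; and "165 subjects shall be enrolled into each of the test group and the control group". From SAP 3.1 and 3.3: three sites, 378 subjects, 189 per arm. Site sizes are not fixed, so 63 per arm per site is assumed, with 94/63/32 and 55/55/55 as the range. Subjects are treated as independent.

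**The plan's own figure.** n = (1.960 + 1.282)² × 2 × 0.98 × 0.02 / 0.05² = 164.8, so 165 per arm. Then 165/0.9 = 183.3, so 184 per arm and 368 in total. Both SAP figures are reproduced.

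**How few failures.** 378 × 0.02 = 7.6 in total; 63 × 0.02 = 1.26 per site-arm; the chance of none in a given site-arm is 0.98^63 = 28%. If the test device's true site differences were -5, +2 and +2 points, Breslow-Day would give P ≤ 0.05 in only 31% of trials.

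**The variance term.** For independent sites and given weights, the variance of Σw·d is Σw²·var. The code uses Σw·var. With three equal sites and w = 1/3, the ratio is var / (var/3) = 3, so the standard error is √3 = 1.73 times too large. The Newcombe terms in the same step use `w_diff**2`, so the block disagrees with itself.

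**Example.** Failures by site: test 0/3/0, control 0/0/3 (3/189 in each arm).

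- Breslow-Day: the common odds ratio is 1. In each of the two sites with failures, the expected count is 1.5 and its variance 1/(2/1.5 + 2/61.5) = 0.732. The statistic is 2 × 1.5²/0.732 = 6.15. P = 0.013 counting only informative sites (1 df), or 0.046 with 2 df. The gate opens either way.
- Site variance: (60/63)(3/63)/63 = 0.000720 at the two sites with failures. At the site with none, the code sets the inverse variance to 1, against 1/0.000720 = 1,389 elsewhere. The weights are 0.0004, 0.4998 and 0.4998.
- As coded: Σw·var = 0.000720; lower limit = 0 - 1.96 × √0.000720 = **-5.26%** (fails).
- Squared weights: Σw²·var = 0.000360; lower limit **-3.72%** (passes).
- Pooled Wald: 2 × (3/189)(186/189)/189 = 0.000165; lower limit **-2.52%** (passes).

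The coding factor here is √(0.000720/0.000360) = 1.41, because the third site carries almost no weight. The remaining distance to -2.52% is the difference between the weighted and pooled estimators.

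**How often, at 98% in both arms** (simulation; 40,000 trials with 1 df, 100,000 with 2 df):

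| | Informative-site df | 2 df |
|---|---|---|
| Gate opens | 4.5% | 3.4% |
| Non-inferiority declared when open: printed code | 53% | 54% |
| squared weights | 91% | 91% |
| pooled Wald | 92% | 90.5% |
| Overall power: SAP as coded | 90.3% | 90.8% |
| Overall power: pooled Wald | 92.1% | 92.0% |

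Cross-check: 4.5% × (92 - 53) = 1.8 points, and 3.4% × (90.5 - 54) = 1.2 points. With 55 per arm per site (2 df), power is 88.4% gated against 89.6% pooled; with 94/63/32 it is 90.9% against 91.8%.

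**When the test cannot be computed.** Either exactly one arm has no failures, so the common odds ratio is 0 or infinite, or both arms have failures but all at one site, so there is nothing to compare. At 98%:

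- One arm only: 0.98^189 = 0.0220; 2 × 0.0220 × 0.9780 = 4.3%.
- One site only: 3 × 0.98^252 × (1 - 0.98^63)² = 3 × 0.00615 × 0.518 = 1.0%.
- Total 5.3%. The exempted all-100% case, 0.98^378 = 0.05%, is not included.

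The other site-size patterns give up to about 9%. If success were 99% or 99.5%, which are assumptions beyond the documents, the share would be about 30% or 54%.

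**The weights.** The code builds `alaph` from `diffn` (difference times n) rather than from the difference, so the weights need not sum to 1. They do in the example above, but came to 0.93 and 0.91 in two others.

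**The case against.** The rule is fully pre-specified, with a numeric threshold and code, and site results are described in every case. A reader might infer that the analysis is chosen after the fact; it is not. It is a preliminary test written down in advance, and the fair criticism is only that the data choose the interval.

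A reader might also infer that the gate itself fails trials with equal results. That is mostly not so. With squared weights, success in gated trials returns to 91%, overall power to 92.0%, and the 3 against 3 example passes. Equal totals then fail only from 6 failures per arm upward (6/189 = 3.2%, above the planned 2%). Even as coded, equal totals that fail make up about 0.16% of all trials.

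Nor is the type I error raised by the gate: at 93% against 98%, non-inferiority is declared in 3.7% of trials gated and 3.9% pooled. The excess over 2.5% belongs to the Wald interval.

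Finally, when the test cannot be computed, pooling would usually give the same conclusion: in those trials pooled Wald passes in 94% at 98% success. All of this stands. It limits the size of the point but removes neither the wrong formula nor the missing rule.

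**Conclusion.** The point holds, at modest size. The weighted branch has an incorrect variance that makes its interval too wide, by 1.41 in the example and by up to about 1.73 with three equal sites. It can fail a trial with 3 failures in each arm. At the planning rates the branch is entered in about 3.5 to 4.5% of trials and the average loss of power is about 1 to 2 points. The error is conservative, and most of the harm comes from the variance term rather than from the gate.

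Separately, about 5% of trials at 98% success would have no Breslow-Day result and no stated branch. The reading that the primary analysis is undefined in a third or half of trials needs success rates of 99% or 99.5%, which the documents do not give.

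These figures rest on equal site sizes, independent subjects and equal true rates. The gate frequency and the example's P value also depend on the degrees-of-freedom convention, which the SAP does not state.

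**What to change.** Preferred: delete the gate. Pre-specify one primary rate-difference interval suited to rates near 100%, for example a site-stratified Miettinen-Nurminen interval with Mantel-Haenszel weights. This agrees with the single interval in Protocol 6.4. Report results by site descriptively, on the rate-difference scale.

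If the weighted branch is kept:

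1. Change the variance to `sum(w_diff**2*var)`.
2. Check that the weights sum to 1, starting with the use of `diffn` in `alaph`, and review the inverse variance of 1 given to sites with no failures.
3. State that sites are pooled when Breslow-Day cannot be computed, and state the degrees of freedom.
4. Reconcile the text, which first rules out combining sites and then combines them, and align SAP 6.3.1 with Protocol 6.4.

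Either route costs SAP wording and a few lines of code, to be settled before the analysis. Trial conduct, data collection and sample size do not change.

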18.1 Basic document management
18.2 Finance and insurance
Investigator's Statement

Abbreviations	Definition	
AE	Adverse Event	
CRC	Clinical Research Coordinator	
CRO	Contract Research Organization	
D	Day	
DMP	Data Management Plan	
eCRF	Electronic Case Report Form	
EDC	Electronic Data Collection	
FAS	Full Analysis Set	
GCP	Good Clinical Practice (Medical Device)	
ICF	Informed Consent Form	
MedDRA	Medical Dictionary for Regulatory Activities	
mL	Milliliter	
NMPA	National Medical Products Administration	
PASS	Power Analysis and Sample Size (Statistics Software)	
PPS	Per Protocol Set	
PT	Preferred term	
SAE	Serious Adverse Event	
SAS	Statistical Analysis System (Statistics Software)	
SOC	System Organ Class	
SS	Safety Set	
°C	Celsius	

List of Abbreviations

Synopsis

Study Title	A Prospective, Multi-center, Randomized, Open-label, Parallel-controlled Clinical Study of Pre-filled Flush Syringes
Protocol No.	MDS-21FLUSHCN01
Sponsor	BD Medical Technology (Jiangsu) Co., Ltd.
Study Sites	3 study sites
Planned Study Period	April 2022 to September 2023
Subject Population	Subjects requiring locking and flushing the end of catheter line at the intervals of different drug treatment.
Study Objective	To compare the BD PosiFlush [™] Pre-filled Flush Syringes (manufactured by BD, USA) with the pre-filled flush syringes (manufactured by BD Medical Technology (Jiangsu) Co., Ltd.) and evaluate the effectiveness and safety for locking and flushing the end of catheter line.
Study Design	This prospective, multi-center, randomized, open, and parallel- controlled clinical study is intended to evaluate the effectiveness and safety of pre-filled flush syringes. After signing of informed consent form, all subjects who meet the inclusion criteria and do not meet the exclusion criteria are randomized
	into the investigational group or control group in a 1:1 ratio. This study is performed by 63 trial nurses using the study device (investigational device and control device) to lock and flush the end of catheter line for all subjects, each nurse will randomly use 3 investigational devices and 3 control devices.
Number of subjects planned to be enrolled	 Sample size calculation assumptions: Overall performance success rate in the investigational device group is 98% Overall performance success rate in the control device group is 98% Non-inferiority margin is 5%
	 Allocation ratio of 1:1
	• Type I error rate is 0.025 one-side
	• Power is 90%
	• Attrition rate is 10%

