6.1 Estimation of sample size

A total of 378 subjects are proposed to be enrolled in this clinical trial. This study is a non-inferiority design with parallel control. The equivalent products already available on the market (BD Pre-filled Flush Syringes) are selected as the control group device. The study intends to investigate that the overall performance of the investigational device group device for flushing and/or locking the catheter is non-inferior to that of the control group device. According to previous clinical experience, the overall performance success rate of equivalent devices for flushing and/or locking catheters is about 98%. Hence, it is assumed that the treatment completion rate of the investigational device group is consistent with that of the equivalent device. This study adopts a non-inferiority design, with α =0.025 (one-sided), β =0.1 (power of test of 90%), and the non-inferiority margin of 5%. The subjects in the investigational device group and the control group are allocated in an equal ratio of 1:1. The sample size shall be calculated to each enroll 165 subjects into the investigational device group and the control group by using the PASS software. However, 368 subjects shall be included to participate in this clinical study considering factors such as drop-out of subjects (drop-out rate of 10%) during the trial and other factors.

This study will be performed by 63 authorized nurses who participate in using the study device, each nurse will randomly use 3 investigational devices and 3 control devices, so a total of 378 subjects will be proposed to be enrolled in this clinical trial.

Minimum and maximum number of subjects and reasons for each clinical trial institution

This trial will be conducted simultaneously in multiple clinical trial institutions to enroll subjects. In principle, the subjects enrolled at each site will be distributed as evenly as possible to ensure adequate site representation. However, given the feasibility and enrollment progress, the number of subjects enrolled at each site will be properly adjusted according to the actual situation, so as to ensure the relative balance of the enrollment size of each site, and the final enrollment size of a particular site shall not exceed 50% of the total number of cases, and at least not less than half of the number of cases borne by the average distribution.

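### The Wald interval behind the primary non-inferiority decision gives a one-sided error of about 4 to 5% at 98–99% success, not the stated 2.5%

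*SAP*

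**What the plan says.** The error rate is fixed in three places. The Protocol Synopsis has "Type I error rate is 0.025 one-side". Protocol 6.1 plans "with α =0.025 (one-sided), β =0.1 (power of test of 90%), and the non-inferiority margin of 5" per cent, and SAP 3.2 repeats these values. Both documents assume 98% success in each arm.

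Protocol 6.4 asks for a two-sided 95% interval for the rate difference and names no method. SAP 6.3.1 supplies one. A Breslow-Day test across sites comes first. If P > 0.05 the sites are pooled, and if P ≤ 0.05 a site-weighted (minimal risk) difference is used. In both branches "the 95% confidence interval (CI) for the difference in the pass rate between the two groups is calculated using the Wald method". There is one exception: "If the pass rate is 100% in both groups, the Newcombe Wilson method" is used instead. Non-inferiority is concluded if the lower limit is above -5%. Neither document reports the error rate that this rule achieves.

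**The concern.** The Wald interval takes its variance from the observed proportions. Near 100% that variance shrinks with the number of failures, so the interval is narrowest when the test arm has few failures by chance. Those are the results on which a device at the margin would be passed.

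SAP 6.1 reserves confirmatory inference for the primary indicator, and this interval alone settles it in a premarket registration trial. If the interval is too narrow, a device 5 points worse than control is accepted more often than the plan states, and the quoted power is partly bought with that excess error.

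The exception at 100% in both arms shows that the SAP knows Wald fails at the extreme, but it repairs a single outcome and leaves its neighbours unrepaired.

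**Working it through.** **Inputs.** One-sided alpha 0.025, power 90%, margin 5 points, 98% success in both arms, 1:1 allocation, 165 per arm before dropout, 368 in total after 10% dropout, 378 enrolled (Protocol 6.1, SAP 3.2). This gives 378/2 = 189 per arm, and 189 × 0.9 ≈ 170 per arm after 10% loss. Control rates other than 98% are assumptions, used to show the range.

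**The plan's own figure.** n = (1.96 + 1.2816)² × 2 × 0.98 × 0.02 / 0.05² = 164.8, so 165 per arm. Then 165/0.9 = 183.3, so 184 per arm and 368 in total. Both figures reproduce. This formula uses the same unpooled variance as the Wald interval.

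**Formulas.**
- Wald lower limit: d − 1.96 × √[p₁(1−p₁)/n + p₂(1−p₂)/n], with d = p₁ − p₂.
- Newcombe-Wilson lower limit: d − √[(p₁ − l₁)² + (u₂ − p₂)²], where l₁ and u₂ are the Wilson lower limit for test and upper limit for control.

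**Error at the boundary.** All pairs of success counts were enumerated. The SAP rule was applied (Wald; Newcombe-Wilson if both arms are at 100%; pass if the limit exceeds -5%), and exact binomial probabilities were summed with the true test rate 5 points below control.

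| Control rate | n=165 | n=170 | n=184 | n=189 |
|---|---|---|---|---|
| 95% | 3.0% | 3.0% | 2.9% | 3.0% |
| 98% (planned) | 4.1% | 3.8% | 3.8% | 3.9% |
| 99% | 5.2% | 4.5% | 4.4% | 4.5% |
| 99.5% | 6.0% | 5.2% | 4.8% | 5.4% |

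With Newcombe-Wilson throughout, the error at control rates of 98%, 99% and 99.5% is 2.1%, 1.9% and 1.8% with 189 per arm; 2.4%, 2.2% and 2.1% with 184; and 2.1%, 1.9% and 1.6% with 170.

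**Why it happens.** Take 7 test and 4 control failures of 189 each. Then d = −3/189 = −1.59 points. The Wald standard error is √[(7×182 + 4×185)/189³] = 1.73 points, so the limit is −1.59 − 1.96 × 1.73 = −4.97 and the device passes. The true standard error at 93% v 98% is √[(0.93×0.07 + 0.98×0.02)/189] = 2.12 points. The Newcombe limit for this table is −5.55, and the device fails.

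**Which decisions change.** Largest number of test failures, of 189, that still passes:

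| Control failures | 0 | 1 | 2 | 3 | 4 | 5 | 6 |
|---|---|---|---|---|---|---|---|
| SAP rule | 5 | 5 | 5 | 6 | 7 | 7 | 8 |
| Newcombe-Wilson | 3 | 4 | 4 | 5 | 6 | 6 | 7 |

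At 98% success the expected number of failures is 0.02 × 189 = 3.8 per arm, so these tables lie where the data are expected to fall.

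**The switch.** 189/189 v 189/189 gives a Newcombe lower limit of −1.99%. 188/189 v 189/189 goes to Wald and gives −1.56% (Newcombe would give −2.94%). One added test failure improves the test device's bound.

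**Power with equal true rates.**

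| Rates | n per arm | SAP rule | Newcombe-Wilson |
|---|---|---|---|
| 98% | 165 | 89.8% | 78.7% |
| 98% | 170 | 89.1% | 78.8% |
| 98% | 184 | 91.1% | 84.2% |
| 98% | 189 | 91.9% | 83.6% |
| 99% | 170 | 98.3% | 91.5% |
| 99% | 189 | 99.1% | 95.6% |

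**The site gate.** A simulation of the whole procedure (three equal sites assumed, Breslow-Day gate, site-weighted branch as coded, 100,000 runs) gave 4.0% (165 per arm) and 3.7% (189) at 98% control success, and 5.1% and 4.2% at 99%. The weighted branch was reached in about 3–4% of runs.

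**The case against.** The documents give only one success rate, 98%. There the error is 3.8–4.1%, an excess of about 1.4 points at 189 per arm, and at 95% control success it falls to about 3%. An error of 5% needs a control rate of 99% or more. This is fair as to range: about 4% is the figure for the planned rate, and higher values are conditional. It does not help the rule, which exceeds 2.5% at every sample size considered, with the excess mostly growing as success rises above plan.

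The illustrations can be called selective. Both limits at the switch clear -5% easily, so that anomaly alone changes no decision. Zero control failures has a probability of only 0.98¹⁸⁹ ≈ 2% at the planned rate. Both remarks are correct. But with 1 to 6 control failures the rules still differ by one test failure, and that difference produces the excess error.

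Wald also matches the sample-size formula. That makes the plan internally consistent but does not control the error.

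The strongest point concerns cost. Newcombe-Wilson leaves power below the 90% target at 98%, and restoring it would take about 220 evaluable per arm. That stands. Accepting the lower power or enlarging the trial is the sponsor's choice, and the text should say so openly.

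**Conclusion.** The concern holds. The decision rule in SAP 6.3.1 does not deliver the stated one-sided 2.5%. Over control rates of 98–99% and 165 to 189 per arm, the pooled rule's error is 3.8–5.2%, about one and a half to two times nominal. Still closer to 100% it can be higher, reaching 8.5% at 100% control success with 189 per arm. The Newcombe-Wilson exception gives almost no protection, because 100% in both arms practically never occurs when the test rate is 93–95%. The Breslow-Day gate lowers the error by only about 0.2 points.

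The claimed 90% power at 98% success depends on the same narrow interval. The sample-size arithmetic itself is correct.

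The figures assume equal arms and independent subjects, with no clustering by nurse. This should be corrected before database lock.

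**What to change.** In SAP 6.3.1, use the Newcombe-Wilson interval for every result and remove Wald from the decision rule. Say so for both branches: the pooled interval when Breslow-Day P > 0.05, and the site-weighted Newcombe limit when P ≤ 0.05. The printed code already computes the site-weighted limit beside the Wald one; a pooled Newcombe statement has to be added. A Miettinen-Nurminen score interval is an acceptable alternative. Its error is 1.9–2.2% at 98% control success over 165 to 189 per arm, and its power with 189 per arm is the same 83.6%.

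Restate power for the chosen interval in SAP 3.2 and Protocol 6.1. For Newcombe-Wilson at 98% success it is about 84% with 189 evaluable per arm and 79% with 170; at 99% it is about 96% and 91%.

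The cost is a short text and code change and a less favourable power statement. Correcting the error rate needs no new data and no extra subjects. Keeping 90% power at 98% success would need more, and that is a separate decision for the sponsor.
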